smokeless use in men). Specifically, the main effect and interaction of each biological variable with intervention group will be tested. For each biological variable, statistically non-significant main and/or interaction effects will be omitted from the final analytic models. If there is a significant interaction (indicative of a moderating effect of the characteristic), the interaction and its component terms will be retained in the final model and a moderator analysis will be conducted applying the approach recommended by Kraemer et al.⁵¹ for clinical trials. For example, if there is a significant sex-by-group interaction effect, the moderating effects of sex will be further evaluated by testing for intervention effects within subgroups of the characteristic. We realize that our numbers of projected females for this study are small given nationally females use smokeless tobacco a very low rate (0.5%)¹¹ and our pilot mirrored these results. Nonetheless, we will conduct analyses to address the influence of these biological factors on study outcomes if there is adequate heterogeneity of the characteristic to do so.

[figure not shown]
Aim 1 Statistical Analysis. We will use logistic regression without covariates to test for an intervention group difference (SGR vs control) in self-reported cessation at 6 months. Next, a covariate-adjusted analysis will also be conducted to evaluate identified potential baseline covariates and examine the impact of biological variables (e.g., age and sex and their interaction with group) on self-reported cessation at 6 months. Odds ratios (ORs) and their 95% CIs will be used to estimate effect size and address clinical significance. As a supplemental analysis, Generalized Estimating Equation (GEE) models for longitudinal binary outcomes will be used to test for intervention group differences in cessation trajectories across the 6 months, with *a posteriori* contrasts at each assessment point. Finally, we will compare self-reported and biochemically confirmed cessation outcomes obtained from 20% random sample of those who self-reported cessation at end of treatment and month 3 and 6. A z-test will be used to test for a group difference in the percent agreement at each time point.

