Aim 2 Statistical Analysis. We will use hierarchical mixed-effects models for repeated measures with *a posteriori* contrasts at each time point to test for intervention group differences in the trajectory of changes in severity of craving, withdrawal, self-regulation, and restraints across time (baseline, end of treatment, 3 and 6 months post-intervention). Specifically, random coefficients regression model (RRM) for longitudinal data will be used to compare the rate and pattern of change of these outcomes across time. Fixed effects will be intervention group, time, and group-by-time, while random effects will be participant and participant-by-time. A covariate-adjusted analysis will also be conducted to evaluate the influence of baseline covariates and biological variables (e.g., age and sex effects and their interactions with group). The model will be fitted for significant non-linear change within one or both intervention groups. Intraclass coefficients across time along with Cohen *d* equivalents and their 95% CIs at each time point will be used to address intervention effect sizes.

Exploratory Aim 3 Statistical Analysis. We will conduct mediator analyses using criteria recommended by Baron and Kenny⁵² as well as analytic guidelines from Kraemer et al.⁵¹ to explore whether changes in withdrawal symptoms, craving, self-regulation, and restraint mediate intervention group effects on tobacco use cessation across the 6-months. Each proposed mediator

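### In Aim 2 the age and sex moderator test leaves out time, so it averages in the baseline visit, dilutes any moderation of change, and may then be dropped

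*SAP*

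**What the plan says.** The SAP's Aim 2 Statistical Analysis sets out to "test for intervention group differences in the trajectory of changes in severity of craving, withdrawal, self-regulation, and restraints". Four outcome visits enter this comparison, and the first of them precedes treatment: "across time (baseline, end of treatment, 3 and 6 months post-intervention"). Baseline is therefore a response occasion in the model and not only a covariate. The model is stated as follows: "Fixed effects will be intervention group, time, and group-by-time, while random effects will be participant and participant-by-time". The part of it that carries the intervention effect on change is group-by-time.

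For the covariate-adjusted version, the same section will "evaluate the influence of baseline covariates and biological variables (e.g., age and sex effects and their interactions with group").

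The general rule is in the SAP section Consideration of Biological Variables: "Specifically, the main effect and interaction of each biological variable with intervention group will be tested". It continues that "statistically non-significant main and/or interaction effects will be omitted from the final analytic models". A significant interaction is kept and opens a moderator analysis with tests of the intervention effect within subgroups. Neither section mentions an interaction of age or sex with both group and time.

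**The concern.** For Aim 1 there is one outcome at one visit (cessation at month 6), and characteristic-by-group is the right moderator term. Carried unchanged into the Aim 2 repeated-measures model, the same term means something else. It says that the gap between arms varies with age by the same amount at every visit, including the one before treatment. It does not ask whether the effect on change varies with age.

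This term also decides what happens next: it is omitted if non-significant, and subgroup work follows only if it is significant. A diluted test can therefore lose a real age moderator of craving, withdrawal, self-regulation or restraint. If the term is kept, its coefficient understates the moderation of change.

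**Working it through.** **The plan's own figure.** The only power figures are for Aim 1. With 250 per arm, 25% vs 12% and two-sided 0.05, the pooled proportion is 0.185. The null SE is √(2 × 0.185 × 0.815 / 250) = 0.0347 and the alternative SE is √((0.1875 + 0.1056) / 250) = 0.0342. Then (0.13 − 1.96 × 0.0347) / 0.0342 = 1.81, which gives 96.5% power and agrees with the stated 96%. No power is given for Aim 2 or for moderation.

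**Inputs.** From the SAP: 500 participants allocated 1:1, two-sided 0.05, four visits, random intercept and slope. Assumed, because the documents give no values:
- baseline SD 1
- random-intercept and residual variances 0.5 each, so a correlation of 0.5 without random slopes
- slope SD 0 to 0.10 per month, uncorrelated with the intercept
- visits at t = 0, 1.5, 4.5 and 7.5 months (end of treatment taken as the end of the 6-week reduction)
- true moderation of 0.3 SD per SD of age by month 6
- no dropout

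**Two patterns of true moderation**, as fractions of the month-6 value: constant after baseline, m = (0, 1, 1, 1); linear build-up, m = (0, 0.2, 0.6, 1).

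**Planned term.** Let V be the 4 × 4 covariance matrix of the visits. A constant characteristic-by-group coefficient weights the visits by w = V⁻¹1 / (1′V⁻¹1). Its expectation is 0.3 × w′m. With arms coded ±0.5, its SE is √(4 / (500 × 1′V⁻¹1)).
- Slope SD 0: w = (0.25, 0.25, 0.25, 0.25) and 1′V⁻¹1 = 4 / 2.5 = 1.6, so SE = 0.0707. Constant: 75% recovered, z = 0.225 / 0.0707 = 3.18, power 89%. Linear: 45% recovered, z = 0.135 / 0.0707 = 1.91, power 48%.
- Slope SD 0.10: w = (0.39, 0.33, 0.20, 0.08), SE = 0.0745. Constant: 61% recovered, z = 2.47, power 69%. Linear: 27% recovered, z = 1.09, power 19%.

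As the slope variance grows, baseline, where there is nothing to find, takes the largest weight.

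**Alternatives under the same assumptions.**
- Three-way, categorical visits, 3 df: noncentrality δ′S⁻¹δ, where δ is the vector of moderation of change at the three later visits and S its covariance. It is 16.9 to 13.8 (constant) and 13.3 to 8.0 (linear).
- Characteristic-by-group on mean post-baseline change: SE 0.0730 to 0.0834. Constant: z = 0.3 / SE = 4.11 to 3.60. Linear: the mean of (0.2, 0.6, 1) is 0.6, so z = 0.18 / SE = 2.47 to 2.16.
- Three-way, linear time: SE of the month-6 value 0.0823 to 0.1062. Constant: 76% recovered, z = 0.229 / SE = 2.78 to 2.16. Linear: z = 0.3 / SE = 3.65 to 2.82.

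| Test | Power, constant after baseline | Power, linear build-up |
|---|---|---|
| Planned: characteristic × group | 69-89% | 19-48% |
| Three-way, categorical visits (3 df) | 89-95% | 65-88% |
| Characteristic × group on mean change | 95-98% | 58-69% |
| Three-way, linear time | 58-79% | 81-95% |

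**Check with dropout.** A small mixed-model simulation (60 runs per pattern, 30% dropout, true value 0.30) compared the planned term with the linear-time three-way term. Linear build-up: mean estimate 0.095 and 32% significant for the planned term, against 0.287 and 83%. Constant after baseline: 0.183 and 70%, against 0.252 and 67%.

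**The case against.** **The wording may be shorthand.** The Aim 2 sentence gives examples and describes an adjusted version of a model whose effect is already a trajectory difference, so an analyst might add time unprompted. That is possible, but the general rule names only the interaction with group as the term to be tested, and a pre-specified plan should not leave that term to be chosen later.

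**Removal is not certain.** A reader might infer that a real moderator will be dropped. The figures do not support that: in the constant case the planned term is significant, and so kept, 69-89% of the time.

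**The planned test is not always weaker.** A reader might infer that any three-way term would do better. With linear time, the natural form in a random-coefficients model, it has less power than the planned term when moderation is constant after baseline (58-79% against 69-89%). The 95-98% figure belongs to the analysis of mean change, not to a three-way test. If intercepts and slopes are negatively correlated (−0.4, slope variance 0.5 at the last visit, moderation 0.25 SD, constant after baseline), the planned term has 78-80% power, against 63% for a categorical baseline-to-month-6 contrast. Its estimate is still diluted there, to 72-74% of the true value. So dilution is the general finding, and the loss of power depends on the pattern.

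**A kept term is not the end product.** The SAP follows a significant interaction with intervention effects within subgroups, and Aim 2 reports contrasts at each visit. This limits the harm from a diluted coefficient, provided that the follow-up uses differences in change.

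**Little rests on it.** This stands. Aim 2 is secondary, and no hypothesis of moderation by age is stated. The pilot was 97% male, which would mean about 15 women in 500 (0.03 × 500), and the SAP already makes these analyses conditional on adequate heterogeneity.

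**Conclusion.** The point holds as a mismatch between the Aim 2 effect (group-by-time, baseline included as an outcome) and the moderator term named for it (no time). As written, the test does not ask whether the effect on change depends on age or sex, and its coefficient was attenuated in every scenario tried.

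Under the stated assumptions it recovers about 61-75% of moderation that is constant after baseline and 27-45% of moderation that builds linearly. The loss of power is severe in the linear case and moderate in the constant case. All these sizes rest on variances, visit times and a moderation effect that the documents do not give; the direction of the dilution does not.

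The importance is low. The point concerns mainly age, in the adjusted analysis of a secondary aim. A reader might take it as a threat to the trial's main result, but Aim 1 uses a single visit, its characteristic-by-group term is correct, and its power is unaffected.

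**What to change.** Add one sentence to the SAP: for Aim 2, the moderator test and the retention rule apply to characteristic × group × visit, with visits categorical and all lower-order terms kept, including characteristic × visit. Testing characteristic × group on change from baseline is an acceptable alternative. Choose one in advance, because the table shows that neither form is best under both patterns, and state the form of time.

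Base any Aim 2 subgroup follow-up on arm differences in change from baseline. Keep characteristic × group for the single-visit Aim 1 outcome.

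No new data are needed. The cost is a few more model terms.

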Summary. Rural and medically underserved smokeless tobacco users represent a vulnerable group for tobacco use. Despite their high risk for tobacco-related cancers, underserved smokeless tobacco users have not been widely targeted for cessation intervention trials. Text-based interventions have the potential to consistently reach many more underserved smokeless tobacco users compared to both clinic-based and web-based interventions. Our SGR intervention has the potential to increase quit rates compared to the current standard of care as our SGR intervention addresses common barriers (withdrawal symptoms and situational and environmental chewing cues) to quitting. Our pilot work supports the feasibility and acceptability of a text-based smokeless tobacco cessation intervention approach. *The proposed study has public health relevance as it will determine if our intervention performs better than standard of care and is worthy of larger scale dissemination, will add to evidenced-based cessation treatments for smokeless tobacco users and shed light on the important mechanisms of intervention effects in this understudied group of tobacco users.*

2. Innovation

The proposed project has the potential to improve the health of underserved smokeless tobacco users and will have implications for future tobacco cessation initiatives in rural and underserved communities. This project is innovative for multiple reasons.

- We propose one of the first large-scale studies using SGR aimed at an underserved group of tobacco users. Therefore, this study aims to decrease a tobacco-related health disparity by decreasing rates of use and bringing innovative interventions to those with limited access.

- Our study is innovative in that it is the first RTC to compare a text-based reduction intervention to a standard of care intervention. The results of this innovative study have public health relevance and can be used to determine if our SGR intervention should be disseminated broadly.
- Our study will explore mechanisms of cessation intervention effects to expand the limited literature in the field on this area. This information will provide valuable data on important intervention targets that can be used to inform future more targeted treatment strategies in this group of tobacco users

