will be evaluated separately (See **Figure 5**). First, the initial step of the formal mediation analysis will be to determine whether the intervention group significantly influences the trajectory of change in withdrawal symptoms, craving, self-regulation, and restraint (Path A). The Path A analysis will be completed in Aim 2. Second, logistic regression will be used to examine whether the slope coefficients for the individual trajectories of the proposed mediator are associated with cessation at 6 months (Path B). The final logistic regression model conducted for Aim 1 will be used to test for intervention group differences in cessation at 6 months post-intervention (Path C). Finally, the slope coefficients for the proposed mediator will be added as a covariate to the Path C logistic regression model (Path C'). The Path C' analysis will allow us to examine the effects of the intervention groups on Month 6 cessation after adjusting for the effects of change in the proposed mediator across time. For each proposed mediator of SGR effects, mediation will be established if the SGR group compared to the control group has significantly greater improvements in the mediator as an outcome (Path A), the degree of improvements in the mediator across time is related to cessation at 6 months (Path B), the SGR group has a significantly higher cessation rate at 6 months compared to the control group (Path C), and SGR effects on cessation are partially or fully diminished after adjusting for the mediator effect (Path C'). A Sobel's Test will be used to further determine the degree to which improvement in withdrawal, craving, self-regulation, and restraints mediate intervention effects. ORs and their 95% CIs will provide estimates of effect sizes.

Figure 5: Mediation Analysis Pathways

Statistical Power. The sample size of 500 (N=250 per intervention arm) will provide at least 90% power to address the primary aim (Aim 1), primary outcome (self-reported cessation at 6 months), and primary analysis (ITT analysis). A previous smokeless tobacco SGR study in smokeless tobacco resulted in a 27% cessation rate at 6-months.²⁵ Our pilot resulted in a 22% cessation rate at 6-months. Given the improvements to our

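### Because Aim 3 tests each mediator alone, a measure that SGR improves and that correlates moderately with a true mediator can be called established without affecting quitting

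*SAP*

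**What the plan says.** The SAP's Exploratory Aim 3 Statistical Analysis sets out to "explore whether changes in withdrawal symptoms, craving, self-regulation, and restraint mediate intervention group effects on tobacco use cessation". Each proposed mediator "will be evaluated separately".

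The rule has four parts.
- **Path A:** "mediation will be established if the SGR group compared to the control group has significantly greater improvements in the mediator as an outcome".
- **Path B:** the individual slopes of that one mediator predict cessation at 6 months in a logistic regression. Neither arm nor the other mediators are mentioned in this step.
- **Path C:** SGR has a significantly higher 6-month cessation rate than control.
- **Path C′:** the SGR effect shrinks, partly or wholly, once that mediator's slope is added. No threshold or test is given.

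A Sobel test follows, to describe the degree of mediation; it is not listed as a condition. The opening of the Data Analysis Plan sets a two-sided 0.05 level, left unadjusted for the mediation steps because they are exploratory. The protocol's Innovation section says of the mechanism work: "This information will provide valuable data on important intervention targets".

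**The concern.** The question for each measure is whether it carries the SGR effect. A model with one mediator slope answers a looser question: whether that measure, or anything correlated with it, predicts quitting. If SGR improves two correlated measures and only one drives quitting, the other borrows its association. Adding arm to Path B does not remove this, because the confounder is the other mediator. Adjusting alpha for multiplicity does not remove it either.

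The conditions are ones the trial itself expects. The protocol's Overall Strategy makes change in all four measures a secondary aim. Its Significance section links them, describing users who handle cravings by exercising restraint. If SGR works as hoped, Path A will not reliably screen out a passive measure.

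What is at stake is the reading of Aim 3. A list of established mediators could point later interventions at a measure that does nothing by itself.

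**Working it through.** **1. The plan's own figure.** The Statistical Power section gives 250 per arm, 25% vs 12%, two-sided 0.05, 96% power. The mean rate is 0.185, so

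z = [0.13 × √250 − 1.96 × √(2 × 0.185 × 0.815)] / √(0.25 × 0.75 + 0.12 × 0.88) = (2.056 − 1.076) / 0.541 = 1.81,

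and power is Φ(1.81) = 96.5%. The stated 96% is reproduced, as are the odds ratio, (0.25/0.75)/(0.12/0.88) = 2.44, and its d equivalent, ln(2.44) × √3/π = 0.493. Under the planning assumptions Path C is therefore nearly always met and screens out little. The documents give no error rate for the mediation rule.

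**2. Why a passive measure passes.** Let M1 be a true mediator with log-OR b per SD and SGR shift a1. Let M2 have no effect on quitting, SGR shift a2, and within-arm correlation r with M1. Then E(M1 | arm, M2) = a1·arm + r(M2 − a2·arm). With M1 left out, M2 takes a coefficient of about b·r, and the arm coefficient falls by about b·r·a2 (approximate, since the logistic link shrinks both somewhat). With b = 0.8, r = 0.5 and a2 = 0.4, M2 shows a log-OR of about 0.40 and the arm coefficient falls by about 0.16. Paths B and C′ are both satisfied by a measure that does nothing.

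**3. How often.** Monte Carlo, 250 per arm, marginal quit rates held at 12% and 25%. Established means Paths A, B and C each have z > 1.96 in the favourable direction and the arm coefficient is smaller in C′ than in C. The shifts, log-ORs and correlations are assumptions. Slopes are drawn as normal variables, with no missing data. Monte Carlo error is about 1.5 points, and independent runs agree to within a few points.

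| How SGR moves the inert measure | Inputs (shift, log-OR) | r = 0.3 | r = 0.5 | r = 0.7 |
|---|---|---|---|---|
| As much as the true mediator | 0.4 SD, 0.8 | 67% | 93% | 95% |
| As much as the true mediator | 0.3 SD, 0.6 | 47% | 74% | 88% |
| Only through the true mediator (a2 = r·a1) | 0.4 SD, 0.8 | 19% | 54% | 86% |
| Only through the true mediator (a2 = r·a1) | 0.3 SD, 0.6 | 8% | 31% | 61% |
| Not at all (a2 = 0) | range over runs | 1–3% | 1–3% | 1–3% |

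**4. Variations, equal shifts.**
- Taking the mediator's coefficient from the arm-adjusted model instead of the unadjusted Path B still leaves about 30–95%.
- Also requiring a significant Sobel test gives 15%, 39% and 65% at r = 0.3, 0.5 and 0.7 with 0.3 SD and log-OR 0.6. With 0.5 SD and log-OR 1.0 it gives 52%, 92% and 97%.
- With 175 per arm (0.5 SD, log-OR 1.0) the rule gives 67%, 85% and 88%.

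**5. What a joint model does.** With both slopes and arm in one model and error-free slopes, the inert measure is declared in at most about 3% of trials, and the true mediator is still found in 81–97%. With slope reliability 0.6 (log-OR 1.0, equal shifts), the inert measure is still declared in 8–34% (0.3 SD) or 12–43% (0.5 SD) as r goes from 0.3 to 0.7.

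**The case against.** **Correlation alone is not enough.** A reader might infer that any measure merely correlated with a true mediator will be declared a mediator in most trials. The documents do not support that. Path A requires a significant SGR effect on the measure itself, and without one the rate is 1–3%. Nor is *most trials* a property of the plan: it depends on the shift, the association and the correlation, none of which the documents give. With a small shift passed on through the true mediator, or with low correlation, the rate is well under half. This objection stands and sets the limits of the point.

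**The joint model is not a neutral referee.** Suppose SGR raises restraint, restraint lowers craving, and craving drives quitting. Restraint is then a real mediator, yet adjusting for craving removes its coefficient. In simulation with both measures shifted equally, the SAP rule finds such an upstream mediator in 47–96% of trials; a joint-model rule finds it in 1–3%. The simulated data have the same distribution as in the inert-measure case, so statistics alone cannot say which is true. If all four measures contribute modestly (log-OR 0.3 each, 0.4 SD shift), detection per mediator falls from about 96% to about 57%, 45% and 30% at r = 0.3, 0.5 and 0.7. This stands too, and it rules out replacing one gate with the other.

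**Aim 3 is exploratory.** True, and this limits the severity. But the label is used to waive multiplicity adjustment, which is a different matter, and the SAP still sets a rule for calling mediation established.

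The Figure 5 image is not available, so nothing here rests on it.

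**Conclusion.** The concern holds in limited form. The written rule cannot separate a measure that drives quitting from one that SGR also improves and that moves with the driver. Under the assumed inputs the passive measure passes in about 50–95% of trials with equal shifts; the lowest cell is just under half. It passes in about 19–86% when its shift comes only through the true mediator (0.4 SD, log-OR 0.8), and in 1–3% when SGR does not move it. These sizes rest on assumed values and on idealised slopes.

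The defect lies in what a single-mediator result is allowed to establish; the separate models themselves are sound as a first look. The change is worth making because it is cheap and alters what Aim 3 can conclude.

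**What to change.** In the Exploratory Aim 3 section of the SAP:

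1. Keep the four single-mediator analyses.
2. Add one logistic model for 6-month cessation with arm and all four mediator slopes. Report mediator-specific indirect effects with confidence intervals, and the correlations between the mediator slopes.
3. Do not call a measure an established mediator on its single-mediator model alone. Describe that result as consistent with mediation by the measure or by a correlate of it, and the joint-model result as the measure's independent contribution.
4. State that joint-model significance is not the sole gate. It can drop a mediator that acts through another, loses power when several contribute, and only partly corrects when slopes are measured with error.

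The cost is SAP wording, one extra model and wider intervals for individual mediators. No new data or participants are needed, and the Aim 1 analysis and its power do not change.
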